2.9.2 Deaths

Separate summaries for on-treatment and all deaths (including post-treatment death) will be produced by treatment arm, system organ class and preferred term. Additional summary will be displayed to report all deaths up to 150 days after last administration of LAG525/spartalizumab or up to 30 days after the last dose of carboplatin whichever comes last.

All deaths will be listed, post treatment deaths will be flagged. A separate listing of deaths prior to starting treatment will be provided for all screened subjects.

2.9.3 Laboratory data

Laboratory data from all sources (central and local laboratories) will be combined. The summaries will include all assessments available for the lab parameter collected no later than 30 days after the last study treatment administration date (see [Section 2.1.1](#)).

The following summaries will be produced for hematology and biochemistry laboratory data (by laboratory parameter and treatment):

- Worst post-baseline CTC grade (regardless of the baseline status). Each subject will be counted only for the worst grade observed post-baseline.
- Shift tables using CTC grades to compare baseline to the worst on-treatment value
- For laboratory tests where CTC grades are not defined, shift tables using the low/normal/high/(low and high) classification to compare baseline to the worst on-treatment value.

The following listings will be produced for the laboratory data:

- Listings of all laboratory data, with CTC grades and classification relative to the laboratory normal range. Lab data collected during the post-treatment period will be flagged.
- Listing of all CTC grade 3 or 4 laboratory toxicities

Magnesium data from Q2 lab analyzed between 05-Jun-2018 and 09-Jul-2018 and between 22-Nov-2018 and 02-Jan-2019 were excluded because the vendor (Q2 Solutions) identified an issue with serum magnesium (Mg) test results that were analyzed during these two time period. A carryover effect from assays run prior to the Mg tests on those days resulted in an increase of measured Mg test results. Hence, the Mg test results reported during these times may have been inaccurately increased and therefore should be considered as unreliable.

For the biochemistry data, two versions of the tables will be produced. One version will include all data and another version will exclude unreliable magnesium data.

Liver function parameters

Liver function parameters of interest are total bilirubin (TBL), ALT, AST and alkaline phosphatase (ALP). The number (%) of subjects with worst post-baseline values as per [Novartis Liver Toxicity guidelines](#) will be summarized:

The following summaries will be produced:

- ALT or AST > 3xULN
- ALT or AST > 5xULN
- ALT or AST > 8xULN
- ALT or AST > 10xULN
- ALT or AST > 20xULN
- TBL > 2xULN
- TBL > 3xULN
- ALT or AST > 3xULN & TBL > 2xULN
- ALT or AST > 3xULN & TBL > 2xULN & ALP < 2xULN (potential Hy's law)

Potential Hy's Law events are defined as those subjects with concurrent occurrence of ALT or AST > 3xULN and TBL > 2xULN and ALP < 2xULN in the same assessment sample during the on-treatment period. Further medical review has to be conducted to assess potential confounding factor such as, liver metastases, liver function at baseline etc.

A figure displaying time course of hepatic function tests (ALT, AST, TBL, ALP) in subjects with potential Hy's law will be displayed in the Safety Set. Additionally, evaluation of drug-induced serious hepatotoxicity (eDISH) plots will be produced to display ALT and AST values by TBL values in units of ULN.

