6.1.1.1 Treatment regimen

The recommended dose for the combination of LAG525 + spartalizumab and single agent dose of LAG525 have already been established ([CLAG525X2101C], Section 4.2) and will remain

constant at the established RDE (LAG525 400mg and spartalizumab 300mg both i.v. every 21 days).

Carboplatin will be dosed per AUC 6 given intravenously on day 1 of every 3-week cycle.

All drugs should be given on the same day.

Table 6-2 Dosing regimen

Dose Level	LAG525 (i.v.) mg	spartalizumab (i.v.) mg	carboplatin (i.v.)
Starting Dose	400mg Q3W	300mg Q3W	AUC 6 Q3W

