6.1.5 Treatment duration

Study treatment will continue until the participant experiences one of the following: disease progression per investigator's assessment by RECIST 1.1 (if not meeting the criteria for treatment continuation beyond disease progression as stipulated in Section 6.1.5.1)

, unacceptable toxicity, pregnancy, treatment is discontinued at the discretion of the investigator or the participant, start of a new anti-neoplastic therapy, withdrawal of consent, lost to follow-up, death, or study is terminated by the sponsor.

The investigator may decide to stop carboplatin after 6 cycles, even if the above criteria are not met.

Participants who continue to derive clinical benefit from the treatment based on the investigator's evaluation may receive post-trial access (PTA). PTA means the provision of treatment to trial participants following their completion of this trial (EOT visit will be required prior to PTA). PTA will be provided until one of the following is met: participant no longer derives clinical benefit, investigator discontinues treatment, launch or reimbursement (where applicable), treatment fails to achieve registration in the trial participant's country, or the clinical program is discontinued for any other reason

Mechanisms for provision of PTA may include an extension phase to this study, a separate extension protocol, a rollover protocol, provision of the Novartis investigational product in a non-trial setting (known as post-study drug supply [PSDS]) when no further safety or efficacy data are required, or any other mechanism appropriate for the country.

The PTA mechanism must comply with local laws and regulations in the participating trial countries. If Novartis discontinues the PTA for this trial, Novartis will work with investigators to transition participants onto locally available alternative treatment, or standard of care.

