9.2.1 Follow up for safety evaluations

All participants must be followed for safety up to 150 days after the last dose of LAG525 and/or spartalizumab whichever was stopped last. After the 30-day onsite safety follow-up visit, participants will be followed (via telephone call or onsite visit if participant happens to be visiting the site) at 60 (+/- 7), 90 (+/-7), 120 (+/-7) and 150 (+14) days after the last dose of LAG525 and/or spartalizumab (whichever was stopped last). If carboplatin is stopped more than 150 days after LAG525 and/or spartalizumab, only the 30-day safety follow-up visit needs to be performed.

All safety assessments should be completed as per Table 8-1. However, if the participant begins post treatment antineoplastic medication before the 150-Day safety follow-up visit the collection of new SAEs and AEs unrelated to study medication will stop and thereafter only suspected AEs and suspected SAEs will continue to be collected up to Day 150. Suspected SAEs will continue to be collected beyond the 150-Day safety visit (see Section 16.1 Appendix 1). Data collected should be added to the appropriate eCRF pages. For female participants of child bearing potential, a pregnancy test will be performed at the time points listed in Table 8-1.

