12.5.2 Safety endpoints

For all safety analyses, the safety set will be used. All listings and tables will be presented by treatment group.

Safety summaries (tables, figures) will include only data from the on-treatment period with the exception of baseline data which will also be summarized where appropriate (e.g., change from baseline summaries). In addition, a separate summary for death including on treatment and post treatment deaths will be provided. In particular, summary tables for adverse events (AEs) will summarize only on-treatment events, with a start date during the on-treatment period (treatment-emergent AEs).

The on-treatment period lasts from the date of first administration of study treatment to 30 days after the date of the last actual administration of any study treatment.

The overall observation period will be divided into three mutually exclusive segments:

- Pre-treatment period: from day of participant's informed consent to the day before first dose of study medication
- On-treatment period: from day of first dose of study medication to 30 days after last dose of study medication
- Post-treatment period: starting at day 31 after last dose of study medication.

If dates are incomplete in a way that clear assignment to pre-, on-, or post-treatment period cannot be made, then the respective data will be assigned to the on-treatment period. Additional details to address incomplete AE and/or dosing dates will be addressed in the SAP.

Adverse events

Summary tables for adverse events (AEs) will include only AEs that started or worsened during the on-treatment period, the *treatment-emergent* AEs.

Additional summaries will be displayed to report all AEs, AEs related to study treatment, all SAEs and SAEs related to study treatment collected up to 150 days after last administration of LAG525/spartalizumab or up to 30 days after the last dose of carboplatin whichever comes last.

The incidence of treatment-emergent adverse events (new or worsening from baseline) will be summarized by system organ class and or preferred term, severity (based on CTCAE grades), type of adverse event, relation to study treatment.

Serious adverse events, non-serious adverse events and adverse events of special interest (AESI) during the on-treatment period will be tabulated.

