In case time of assessment (e.g. pre-dose ECG) and time of treatment start is captured, the last available assessment before the treatment start date/time is used for baseline.

For safety parameters (e.g ECGs), where study requires multiple replicates per time point, the average of these measurements would be calculated for baseline (if not already available in the database).

In rare cases where multiple measurements meet the baseline definition, with no further flag or label that can identify the chronological order, then the following rule should be applied:

- If values are from central and local laboratories, the value from central assessment should be considered as baseline.
- If multiple values are from the same laboratory (local or central) or collected for ECGs or vital signs, then the value closest to normal should be considered as baseline.

If subjects have no value as defined above, the baseline result will be missing.

On-treatment assessment/event and observation periods

For adverse event reporting the overall observation period will be divided into three mutually exclusive segments:

1. **pre-treatment period:** from day of subject’s informed consent to the day before first administration of study treatment
2. **on-treatment period:** from date of first administration of study treatment to 30 days after date of last actual administration of any study treatment (including start and stop date)
3. **post-treatment period:** starting at day 31 after last administration of study treatment.

If dates are incomplete in a way that clear assignment to pre-, on-, post-treatment period cannot be made, then the respective data will be assigned to the on-treatment period. Refer to [Section 5.1.2](#) for imputation rules concerning AE start and stop dates.

For other safety data, the on-treatment period will start from the day after the date of first administration of study treatment, unless the time of assessment and time of treatment start is available on the day of study treatment start. For data where time of assessment (e.g. ECGs) and time of treatment start are captured, data collected on the day of first administration of study

treatment at a time before (after respectively) the time of first administration of study treatment will be considered on the pre-treatment period (on the on-treatment period respectively).

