Safety summaries (tables, figures) include only data from the on-treatment period with the exception of baseline data which will also be summarized where appropriate (e.g. change from baseline summaries). In addition, a separate summary for death including on treatment and post treatment deaths will be provided. In particular, summary tables for adverse events (AEs) will summarize only on-treatment events, with a start date during the on-treatment period (*treatment-emergent* AEs). However, all safety data (including those from the post-treatment period) will be listed and those collected during the pre-treatment and post-treatment period will be flagged.

Additional summaries will be displayed to report deaths, all AEs, AEs related to study treatment, all SAEs and SAEs related to study treatment collected up to 150 days after last administration of LAG525/spartalizumab or up to 30 days after the last dose of carboplatin whichever comes last..

Last contact date

The last contact date will be derived for subjects not known to have died at the analysis cut-off using the last complete date among the following:

Table 2-1 Last contact date data sources

Source data	Conditions
Date of Randomization	No Condition
Last contact date/last date subject was known to be alive from Survival Follow-up page	Subject status is reported to be alive, lost to follow-up or unknown
Start/End dates from further antineoplastic therapy	Non-missing medication/procedure term.
Start/End dates from study treatment pages	Non-missing dose. Doses of 0 are allowed.
End of treatment date from disposition page at end of treatment	No condition.
Tumor (RECIST / iRECIST) assessment date	Result is not missing
Verification for treatment beyond RECIST1.1 PD	At least one non missing parameter value
Laboratory/PK/IG collection dates	Was sample taken? = 'Yes'.
Vital signs date	At least one non-missing parameter value
Performance Status date	Non-missing performance status
Start/End dates of AE	Non-missing verbatim term

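### Laboratory tables stop at day 30 after the last dose, so the 30-day safety visit (days 30 to 37) is mostly outside them; one supplementary table would cover it

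*SAP*

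**What the plan says.** Protocol 12.5.2 defines the period that safety tables use: "On-treatment period: from day of first dose of study medication to 30 days after last dose of study medication". SAP 2.1.1 adopts it. The post-treatment period is "starting at day 31 after last administration of study treatment", and "Safety summaries (tables, figures) include only data from the on-treatment period", apart from baseline data and a separate death summary. SAP 2.9.3 applies the rule to laboratory data: "The summaries will include all assessments available for the lab parameter collected no later than 30 days after the last study treatment administration date". Potential Hy's law requires the liver criteria to be met together "in the same assessment sample during the on-treatment period".

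Protocol Table 8-1 schedules hematology and chemistry at the 30-day safety follow-up visit, with a window of -0/+7 days, and at no later visit. Protocol 9.2.1 runs safety follow-up to "150 days after the last dose of LAG525 and/or spartalizumab whichever was stopped last".

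For other safety data the SAP adds summaries beyond day 30: adverse events (2.9.1), AESIs (2.9.1.1), deaths (2.9.2) and concomitant medications (2.4.2). SAP 2.9.3 adds none for laboratory data. Post-treatment values are listed and flagged, and grade 3 or 4 values have their own listing.

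**The concern.** The visit may not be held before day 30, and the tables close on day 30. A sample that every participant in follow-up is scheduled to give is therefore left out of the worst-grade and liver tables unless it is drawn on the first permitted day.

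The protocol gives a reason to look at this sample. Section 6.5.1.2.1 says immune-related events can arise after treatment stops, and section 4.5.2 says they may show only as a laboratory abnormality without symptoms. Under section 10.1.1 a laboratory value becomes an adverse event only if it causes signs or symptoms, is judged clinically significant or needs therapy. Values that meet none of these have no rate by arm after day 30.

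**Working it through.** The plan gives no figure for this point, so there is none to reproduce. The check sets the visit window against the table window.

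**Inputs**
- Visit window: -0/+7 around day 30 (protocol Table 8-1).
- Table cut-off: day 30 inclusive after the last dose of any study drug (SAP 2.9.3).
- Visit anchor: last antibody dose. This is inferred from protocol 9.2.1; Table 8-1 does not state it.
- Randomized: 20, 34 and 34 in Arms 1, 2 and 3 (protocol, Amendment 4).

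**1. Overlap.** Permitted days run from 30 - 0 = 30 to 30 + 7 = 37, which is 37 - 30 + 1 = 8 days. Only day 30 meets the cut-off. Inside: 1/8 = 12.5%. Outside (days 31 to 37): 7/8 = 87.5%.

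**2. When the drugs stop at different times.** If carboplatin is last given k days after the last antibody dose, the cut-off moves to day 30 + k on the antibody clock, and min(8, 1 + k) permitted days are captured:
- k = 0: 1 of 8
- k = 1: 2 of 8
- k = 7: 8 of 8
- k = 21: 8 of 8

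The exposed pattern is an ordinary one. Within a cycle, "All drugs should be given on the same day" (protocol 6.1.1.1), and "The investigator may decide to stop carboplatin after 6 cycles" (protocol 6.1.5), which leaves an antibody as the last drug. Arm 1 has no carboplatin, so its visit is always exposed. If carboplatin stops more than 150 days after the antibodies, protocol 9.2.1 requires only the 30-day visit. That visit would naturally be timed from carboplatin, which returns the count to 1 of 8.

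**3. Share of scheduled draws.** Post-baseline hematology and chemistry draws in Table 8-1 after three cycles: C1D8, C1D15, C2D1, C2D8, C3D1, EOT and the 30-day visit, or 7. After six cycles add C4D1, C5D1 and C6D1, giving 10. At most one draw per participant is affected: 1/7 = 14% or 1/10 = 10%.

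**4. Effect on a rate.** One participant whose worst grade appears only at this visit changes the arm rate by 1/20 = 5.0 percentage points in Arm 1, or 1/34 = 2.9 in Arms 2 and 3, taking all randomized participants to be in the safety set.

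**5. Whether the grade 3 or 4 listing closes the gap.** In SAP Table 5-3, ALT or AST above 3 and up to 5 times ULN is grade 2, as is bilirubin above 1.5 and up to 3 times ULN. A sample on day 33 with ALT 4 x ULN, bilirubin 2.5 x ULN and ALP below 2 x ULN meets the SAP's potential Hy's law thresholds with no grade 3 value. It would be outside the Hy's law count, and those liver values would not appear in the grade 3 or 4 listing. It would still be in the full listing. If confirmed on repeat with no other cause, it would be an SAE under protocol 6.5.2.1.

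**6. Drug exposure at the visit.** Protocol 1.1.3.1.2 gives LAG525 an estimated median terminal half-life of 17 days. Simple exponential decay leaves 0.5^(30/17) = 29% at day 30 and 0.5^(37/17) = 22% at day 37. This is an approximation, since the cited model has two compartments.

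**The case against.** The strongest reply is that this is a pre-specified choice, carried out as written. Protocol 12.5.2 confines safety summaries to the on-treatment period and sets laboratory shifts against the worst on-treatment value; the SAP does the same. That stands, and the day-30 tables should not change.

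The comparison with adverse events is also imperfect. Events are collected to day 150, so a table to day 150 follows naturally, whereas hematology and chemistry have one scheduled draw after EOT. Vital signs and ECOG status are taken at the same visit under the same cut-off, and no change is asked for them. That is a judgement: the protocol names asymptomatic laboratory change as a way immune-related events may appear, and laboratory data carry threshold counts such as Hy's law.

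Most of what matters is caught elsewhere. Investigators must record clinically significant abnormalities, and those recorded as adverse events reach the day-150 tables. Confirmed, unexplained potential drug-induced liver injury is an SAE. What has no rate by arm is mainly asymptomatic, untreated values judged not clinically significant. This stands and keeps the point small.

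Leaving out a visit can only lower worst-grade counts, but that is true of any finite window and does not show bias. Adding the visit can only raise them, including through disease progression; SAP 2.9.3 itself names liver metastases as a possible confounder.

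Finally, at Amendment 4, 85 of 88 participants were off treatment, development in TNBC had been stopped for reasons other than safety, and those moving to post-trial access have only an EOT visit. This limits the practical yield, but not the use of samples already taken.

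**Conclusion.** The point holds as a low-cost improvement to descriptive safety reporting. When an antibody is the last drug given, or all drugs stop together, the only scheduled hematology and chemistry draw after EOT enters the worst-grade and liver tables only if taken exactly on day 30. The textual mismatch is certain. The visit's anchor to the last antibody dose is inferred.

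A reader might infer more, in four ways that the documents do not support:
- *That the SAP departs from the protocol.* It does not; protocol 12.5.2 has the same limit.
- *That 87.5% of visits are lost.* The figure counts permitted days, not visits. The share of visits outside could be anything from 0% (all on day 30) to 100% (none on day 30).
- *That data or important liver signals go unreported.* All values are listed, and clinically significant ones reach the adverse event tables.
- *That the reported rates are known to be too low.* The number of participants whose worst grade appears only at this visit is not given and may be zero.

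Efficacy is unaffected, and SAP section 1 plans no inferential analysis for the close-out report.

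**What to change.** Keep the day-30 tables and add to SAP 2.9.3:

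> One supplementary table by treatment arm will present worst post-baseline CTC grade (hematology and biochemistry) and the liver-parameter categories, including potential Hy's law, using all on-treatment data as defined in Section 2.1.1 plus values from the scheduled 30-day safety follow-up visit, up to day 37 after the last LAG525/spartalizumab dose or, if carboplatin was stopped more than 150 days after the antibodies, up to day 37 after the last carboplatin dose. Of the values added after the on-treatment period, those taken after the start of new antineoplastic therapy (not considering palliative radiotherapy) are excluded; on-treatment values are kept as in the main tables.

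Two details matter. Applying the new-therapy exclusion only to the added values means no count can fall below the main table. The carboplatin clause covers participants whose 30-day visit follows a late carboplatin stop.

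Record the addition in SAP section 4, which now reports no changes. The cost is that entry and one table from data already collected; SAP 2.9.3 already produces a second version of the biochemistry tables because of unreliable magnesium results. The downsides are a window up to 7 days longer than the on-treatment adverse event window, which needs a footnote, and added values that may reflect disease progression.

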2.9.4 Other safety data

2.9.4.1 ECG and cardiac imaging data

At scheduled visits, triplicate 12-lead ECG's will be performed. ECG machines will automatically calculate heart rate and measures of PR, QRS, QT, and QTcF intervals. ECG data will be read and interpreted centrally.

Unscheduled safety ECG’s may be performed at the discretion of the investigator at any time during the study as clinically indicated. Unscheduled ECG’s with clinically significant findings should be collected in triplicate.

Clinically significant abnormalities observed from single 12-lead ECGs collected at the study site are not part of the data analysis described below, but must be reported as adverse events.

ECHO/MUGAs will be performed to assess cardiac ejection fraction. The same procedure (either ECHO or MUGA) should be performed at baseline, follow-up visits if clinically indicated, and at EOT. All ECHO/MUGA assessments will be read and interpreted locally.

Data handling

In case the study requires ECG replicates at any assessment, the average of the ECG parameters at that assessment should be used in the analyses.

Data analysis

The number and percentage of subjects with notable ECG values will be presented by treatment arm.

- QT, QTcF
 - New value of > 450 and ≤ 480 ms
 - New value of > 480 and ≤ 500 ms
 - New value of > 500 ms
 - Increase from Baseline of > 30 ms to ≤ 60ms
 - Increase from Baseline of > 60 ms
- HR
 - Increase from baseline >25% and to a value > 100 bpm
 - Decrease from baseline >25% and to a value < 50 bpm
- PR
 - Increase from baseline >25% and to a value > 200 ms
 - New value of > 200 ms
- QRS
 - Increase from baseline >25% and to a value > 120 ms
 - New values of QRS > 120 ms

A listing of all ECG assessments will be produced by treatment arm and notable values will be flagged. In the listing, the assessments collected during the post-treatment period will be flagged.

For left ventricular ejection fraction (LVEF), a shift table using CTC grades for 'Ejection fraction - decrease' as defined per CTCAE version 5.0 to compare baseline to the worst on-treatment value will be provided:

CTCAE	0	1	2	3	4
-------	---	---	---	---	---

Ejection fraction - decrease	-	-	Resting ejection fraction (EF) 50 - 40%; 10 - 19% drop from baseline	Resting ejection fraction (EF) 39 - 20%; $\geq 20\%$ drop from baseline	Resting ejection fraction (EF) $< 20\%$
------------------------------	---	---	--	---	---

